eCRF	electronic Case Report Form
FOPH	Federal Office of Public Health
GCP	Good Clinical Practice
HRA	Human Research Act (in German: HFG, in French: LRH, in Italian: LRUM)
ICH	International Conference on Harmonisation
ClinO	Ordinance on Clinical Trials in Human Research (in German: KlinV, in French: OClin, in Italian: OSRUM)
SAE	Serious Adverse Event
RCT	Randomized controlled trial
QoL	Quality of life
DGCE	Delayed gastric conduit emptying

1 STUDY SYNOPSIS

Sponsor / Sponsor-Investigator	[name]. med. [name]
Study Title	Patients with Esophageal Carcinoma undergoing Minimally Invasive Ivor Lewis Esophagectomy with or without intraoperative Endoscopic Pylorus Balloon Dilatation: A Randomized Controlled Trial Investigating the Benefits of Intraoperative endoscopic Pylorus Dilatation
Short Title / Study ID	WIDE Trial
Protocol Version and Date	Version 1.3 (18.12.2025)
Study Registration	The study will be registered at www.clinicaltrials.gov and on the Swiss National Clinical Trials Portal (SNCTP) at www.kofam.ch .
Study Category and Rationale	Clinical trial project category A This is a clinical trial investigating the addition of a commonly used intervention to a standard operation in patients undergoing minimally invasive surgical therapy due to esophageal cancer.
Background and Rationale	For esophageal carcinoma, minimally invasive thoraco-abdominal resection is the standard therapy in a curative setting. Delayed gastric conduit emptying (DGCE) is reported in up to 40% of patients after esophageal resection, making it a significant problem in their treatment. DGCE prolongs recovery and hospital stay which in turn increases the overall costs. DGCE or gastroparesis refers to the stomach's inability to empty its contents into the small intestine in a normal timeframe postoperatively. Mechanical stretching of the pylorus has been shown to reduce the incidence of DGCE in retrospective studies. In open surgery, pylorus dilatation was often performed. However, in the era of minimally invasive surgery, mechanical stretching of the pylorus is technically not possible as in open surgery. There is a need for more and stronger evidence to investigate whether mechanical stretching of the pylorus improves the postoperative course of the patients and lowers the postoperative complication rates.
Risk / Benefit Assessment	This study will provide valuable insight into optimising patient care and reducing complications, given the significant burden of esophageal cancer and its treatment. Reducing DGCE with a simple, safe and often used measure such as balloon dilatation of the pylorus would drastically reduce the morbidity of esophagectomy. Since the balloon dilatation would be done at the beginning of the surgery, risks of the intervention are minimal. Measures such as robust safety protocols, informed consent and privacy measures will be used to protect participants throughout the trial to balance the generally occurring risks of the study and to protect all participants from potential harming.
Objective(s)	Our aim is to investigate if intraoperative endoscopic balloon dilatation reduces the incidence of DGCE in the early postoperative course (until three months postoperatively). Furthermore, we investigate if mechanical balloon dilatation reduces the risk for postoperative complications, hospital stay, time to first bowel movement, and improves quality of life (QoL) after esophagectomy.
Endpoint(s)	Primary endpoint: - Incidence of early DGCE in postoperative course (after 5 and 10 days, measured using radiological and clinical parameters) Secondary: - Incidence of late DGCE (after more than 14 days postoperatively) - Rates of anastomotic leak - Complication rates using Clavien Dindo classification - Hospital stays in days - Time to first bowel movement - Time to first solid food intake - Postoperative Quality of life (assessed with the EORTC QLQ-OES18 questionnaire)
Study Design	This study is a single center, double blinded, superiority randomized controlled trial.
Inclusion- / Exclusion Criteria	Inclusion criteria: - Age >18 years - Histologically confirmed esophageal cancer

	
 - Planned surgical resection in curative intent as a minimally invasive Ivor Lewis procedure - Provided informed consent 
Exclusion criteria:
 
 - Prior esophageal or gastric resection - Non-curative intent of surgery - ASA Score V - Patients lacking capacity to provide informed consent
Number of Participants with Rationale	Our hypothesis is that intraoperative endoscopic balloon dilatation of the Pylorus reduces the incidence of DGCE. According to our calculation of the required study size for a power of 80%, we need 52 included patients per study arm. To account for potential dropouts or loss to follow-up, an estimated attrition rate of 10% was considered. Consequently, the final target enrolment is increased to 58 patients per group, leading to a total of 116 patients.
Study Intervention	For patients in the intervention group, a balloon catheter will be inserted orally by experienced gastroenterologists under endoscopic control. The pylorus is then dilated to a predetermined size of 30mm using a standard balloon dilatation kit. The intervention will be performed before the gastric conduit is formed.
Study procedures	All patients are treated according to our internal guidelines for esophageal surgery. Baseline data is collected preoperatively. The relevant information concerning the postoperative course of each patient is retrieved from the specific patient charts. These data are collected by ward physicians who do not have access to the study documents and therefore do not know to which group the patients were randomized. After 5- and 10-days, the output of the nasogastric tube will be assessed. Additionally, a radiological X-Ray to assess the width of the gastric tube will be performed. After 3 months patients are asked to fill out the DGCE symptom questionnaire and EORTC QLQ-OES18 questionnaire for a more detailed assessment concerning DGCE specific symptoms and general GI Symptoms and quality of life. Additionally, a radiological passage will be performed after 3 months.
Study Duration and Schedule	December 2025 - June 2028 all patients included and operated. Follow up for 3 months after last operation to assess late DGCE and QoL.
Investigator(s)	
[name], [name]. med. Clarunis University Digestive Health Care Center [name] phone: mail: [contact]
 
[name], PD Dr. med. Clarunis University Digestive Health Care Center [name] phone: [name] mail: [contact]
 
[name], med. pract. Clarunis University Digestive Health Care Center [name] phone: [name] mail: [contact]

Study Center(s)	Clarunis University Digestive Healthcare Centre
Statistical Considerations:	The statistical analysis is performed according to an intention to treat analysis. Chi-square tests is used for categorical variables and t-tests or Mann-Whitney U tests for continuous variables. Multivariable logistic regression will be used to adjust for potential confounders.
Data privacy	Data are collected from patient's electronic data system (Phoenix®/Meona) at St. Claraspital and the University hospital of Basel. Data is then encoded (from 1 to number of patients) and stored onto a Redcap Database with only personalized access.
Ethical consideration	The aim of this randomized controlled trial (RCT) is to demonstrate that intraoperative endoscopic balloon dilation reduces DGCE, thereby improving quality of life, reducing

	morbidity of the patients, shortening hospital stay and lowering treatment costs in patients with esophageal cancer. Endoscopic balloon dilatation is an established, safe and frequently used method. The risk for complications after balloon dilatation is low.
GCP Statement	This study will be conducted in compliance with the protocol, the current version of the Declaration of Helsinki, the ICH-GCP, the HRA as well as other locally relevant legal and regulatory requirements.

2 BACKGROUND AND RATIONALE

Esophageal cancer is the 8th most commonly diagnosed cancer in the world and ranks 6th on the list of cancer entities leading to death. The two most common subtypes of esophageal carcinoma are esophageal squamous-cell carcinoma (ESCC) and esophageal adenocarcinoma (EAC) (15). These two types differ not only in their cellular origins but also in their geographic prevalence, associated risk factors, and underlying causes. ESCC arises from the squamous cells that line the esophagus. This type of esophageal cancer is more common in low income countries developing world, particularly in regions of Asia and Africa. The high incidence in these areas is linked to several risk factors, the two most important ones are tobacco use and alcohol consumption. EAC develops from glandular cells located in the lower third of the esophagus, often in the context of Barrett's esophagus. This condition involves the transformation of normal esophageal cells into a type more similar to intestinal cells, usually due to chronic acid exposure. EAC is more prevalent in the industrialized world, especially in North America and Western Europe. The primary risk factors for EAC include obesity, Gastroesophageal Reflux Disease (GERD) and smoking (22).

Men are more frequently affected by esophageal cancer than women. The risk of developing esophageal cancer increases with age. Radical surgical removal of esophageal carcinomas is the only curative therapy available today, especially in EAC. However, the operation is associated with high postoperative morbidity and a high complication rate and a 90-day mortality rate of around 4% (17). Thoracoabdominal resection with creation of a gastric tube or, if possible, transhiatal resection are currently the standard operations for esophageal carcinomas (16). Some of the most important postoperative complications after esophagectomy are anastomotic leak, pulmonary complications such as pneumonia and chylothorax, as well as delayed gastric conduit emptying (DGCE) and dysphagia. DGCE refers to impaired or slowed passage of gastric contents through the conduit, leading to prolonged gastric retention after esophagectomy. It causes symptoms such as nausea, vomiting, regurgitation and inability to tolerate oral intake. DGCE is described in up to 40 percent of patients after esophagectomy and therefore presents a great burden in these patients (8,9). The DGCE can put mental and physical stress on these patients. Also, DGCE may increase the risk of anastomotic leaks through the increased pull on the new esophago-gastric anastomosis. Due to the prolonged recovery, the time until discharge from the hospital and start of rehabilitation is significantly delayed as a result of DGCE. The DGCE also results in higher costs which place an additional burden on the healthcare system.

There are various accepted definitions of DGCE. In 2020, a study involving 33 experts in the field of esophageal surgery attempted to develop a universally applicable definition (10). In the study, the experts defined criteria for early DGCE (<14 days postoperatively) as follows: >500 mL daily nasogastric tube output measured on the morning of post-operative day 5 or later, or >100% increase in gastric tube width on frontal chest x-ray along with the presence of an air-fluid level. Experts describe the following parameters for the presence of late DGCE (>14 days postoperatively): The patient should have at least two of the following symptoms: early satiety/fullness, vomiting, nausea, regurgitation or inability to meet caloric needs by oral intake, and delayed contrast passage on upper gastrointestinal radiograph or timed barium swallow. Furthermore, we learned from this study, that the DGCE syndrome can be defined on the basis of the occurrence of symptoms such as nausea or vomiting. In addition, clinical parameters such as the length of time the gastric tube is in place and the flow rate of the gastric tube as well as radiological parameters can be used as diagnostic tools. The DGCE is associated with the gastric tube remaining in place for a longer period of time. In addition, an increased risk for anastomotic leakage and aspiration is described (17). Various techniques for reducing DGCE have been investigated in the past. In former times, surgical pylorus drainage in the form of pyloroplasty or pyloromyotomy was often a standard procedure for distal esophageal resection. In the era of open surgery, the pylorus was often mechanically dilated using regular forceps, this cannot be done in minimally invasive surgery. Since the widespread adoption of minimal invasive surgery, however, these interventions have been performed less frequently. Another technique that was used was the intraoperative injection of Botox into the pylorus. However, this technique did

not show satisfying results in reducing the rate of postoperative DGCE (12). Overall, there is currently no clear evidence regarding the benefits of individual pyloric drainage strategies (13,14). In a large meta-analysis published in 2022 mechanical stretching of the pylorus performed in different ways (manually, endoscopically or by using a forceps) showed a significant reduction in the rate of postoperative DGCE (15). Another meta-analysis by Mohamed Abdelrahman showed that prophylactic balloon dilatation of the pylorus also reduces the incidence of DGCE (20). The current research situation shows varying results and there is still little clear evidence that either technique is superior to prevent the occurrence of DGCE. Therefore, further studies, especially randomized controlled trials, to identify the optimal technique for reducing the rate of DGCE.

Today, where a large proportion of esophagectomies for esophageal cancer are performed using minimally invasive techniques, DGCE is a significant problem. Recently, a study protocol was published describing another RCT investigating prophylactic pyloric dilatation. In this study, however, dilatation is performed one day preoperatively. Early admission of patients increases health care costs unnecessarily. This emphasizes the need for this study, as we still need to find out when and whether prophylactic pyloric dilatation improves patient outcome (21). If it were possible to prove that intraoperative balloon dilatation of the pylorus could significantly reduce the incidence of DGCE, shorten hospital stay and reduce associated complications, this would be a relevant discovery that could further improve the treatment of esophageal cancer in the era of minimally invasive surgery. By providing high-quality evidence on the efficacy of intraoperative balloon dilatation, the study aims to establish a new standard of care for esophagectomy patients. Positive findings could lead to widespread adoption of intraoperative pyloric dilatation. Moreover, this research could pave the way for further studies with greater statistical power on this topic.

3 STUDY OBJECTIVES AND DESIGN

3.1 Hypothesis and primary objective

The central hypothesis of the study is that intraoperative mechanical balloon dilatation of the pylorus performed by endoscopic balloon dilatation reduces the postoperative incidence of early DGCE.

There are various studies investigating the effectiveness of mechanical dilatation of the pylorus in reducing DGCE. In 2022, an RCT was published which investigated the efficacy of intraoperative balloon dilatation versus pyloroplasty versus no pylorus intervention. In this study, however, all patients underwent open surgery and none of the dilatations were performed endoscopically (19). In the era of minimally-invasive surgery we want to find a measure to reduce the incidence of DGCE during the postoperative course. This study would be, to our knowledge, the first RCT of its kind worldwide investigating intraoperative endoscopic balloon dilatation to prevent DGCE in patients with esophageal cancer undergoing minimally invasive surgery. We investigate the effectiveness of intraoperative balloon dilatation in reducing the incidence of postoperative DGCE in patients undergoing minimally invasive esophagectomy for esophageal cancer. In addition, we will detect potential complications associated with intraoperative balloon dilation of the pylorus as well as to prove that intraoperative balloon dilatation reduces DGCE associated complications, for example pneumonia. Furthermore, we want to analyze if the postoperative quality of life is improved in patients with intraoperative balloon dilatation. The findings of this study will make a substantial contribution to surgical practice and patient care in esophageal cancer.

3.2 Primary and secondary endpoints

The Primary outcome is defined as incidence of early DGCE. Early DGCE is defined as presence of a nasogastric tube with an output of >500ml on day 5 or later and/or >100 % increased gastric tube width on radiological chest X-Ray on

day 5 or later (in comparison with baseline X-Ray upon admission on the ICU). DGCE will be diagnosed using both of these mentioned radiological and clinical tools on day 5 and 10 (10).

As secondary endpoints we define the incidence of late DGCE measured using the symptom orientated DGCE questionnaire and a radiological passage examination after 3 months. Furthermore, we want to investigate potential differences between the two groups concerning the rate of anastomotic leaks, postoperative complications such as pneumonia, duration until first bowel movement after surgery, duration until first intake of solid food, presence of vomiting during the postoperative course and length of hospital stay. In addition, we will analyze the quality of life via symptom orientated questionnaires after 3 months using the EORTC QLQ-OES18 questionnaire.

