After inclusion into the study, baseline data will be collected and stored in a study-specific Redcap Database. This Redcap Database fulfills all regulations for a study database. In a next step after the operation, surgery-specific data is collected and stored into the redcap database. The surgical reports will not show whether a patient has received an intervention or not. The relevant information concerning the postoperative course of each patient are retrieved from the specific patient charts. These data are collected by ward physicians who do not have access to the study documents and therefore do not know which group the patients were randomized into. After 5 and 10 days, a radiological X-ray of the chest is performed to assess the width of the gastric tube. After 5 and 10 days we also assess whether a nasogastric

tube is in place and, if so, how high the output of the nasogastric tube is. After 3 months we assess the DGCE specific symptoms using the DGCE symptom orientated questionnaire. We also perform a radiological swallow study to record signs, such as delayed contrast passage for late DGCE. Additionally, patients are asked to fill out the EORTC QLQ-OES18 questionnaire to have a more detailed assessment concerning general GI symptoms.

Safety and Unblinding

In case of adverse events, unblinding will be permissible, and procedures for revealing a participant's allocated intervention will be allowed during the trial, also in case of suspension or premature study termination. Unblinding is done by the Surgeon who attended the operation and is therefore not blinded to the group assignment.

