3.4. Study intervention

For patients in the intervention group, a balloon catheter will be inserted in the pylorus under gastroscopy guidance during the operation while the patient is in general anesthesia for the esophagectomy by an experienced gastroenterologist. The intervention will be performed intraoperatively before the gastric conduit is formed. The pylorus is then dilated to a predetermined size of 30 mm using a standard balloon dilatation kit. The intervention is carried out according to the standard techniques used by our gastroenterologists and presents the current gold standard in the therapy of DGCE. Hence our gastroenterologists are experienced in performing this intervention. The study intervention will only minimally affect the patient since the only addition for the study is the gastroscopy with balloon dilatation of the pylorus. The time for this intervention is around 20 – 30min additionally.

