After the operation all patients are treated according to our internal guidelines for esophageal surgery. Among other things, the guidelines set out standard procedures for oral liquid and food intake, supportive medication, drainage management and gastric tubes. If the course of treatment deviates from the standard, any necessary therapy is adapted according to the patient's needs in consultation with senior physicians. Postoperatively all patients will be transferred to the Intensive care unit for monitoring. The physicians in charge of the intensive care unit then decide when a transfer to the surgical ward can take place. All patients are supported by our physiotherapist as well as our team of nutritionists. We plan to collect the required data as follows. Surgery-specific data is collected using the information from the clinical information system. These include the duration of the operation, intraoperative complications, details of intraoperative balloon dilatation and anaesthesiologic specialties. The relevant information concerning the postoperative course of each patient are retrieved from the specific patient charts. These data are collected by ward physicians who do not have access to the study documents and therefore do not know which group the patients were randomized into. These data include for example gastric tube and chest tube output, interventions and complications, first bowel movement, time of first solid food intake, days of hospitalization and days spend on the intensive care unit as well as data from postoperative imaging. On the 5th and 10th day we carry out a radiological X-Ray examination of the chest assessing the width of the gastric tube and if the width of the tube is increased in comparison to the baseline X-Ray. Furthermore, we assess the output of the nasogastric tube in millilitres. After 3 months every patient will be seen in our surgical consultation for a routine check-up. There the patients will fill out the DGCE Symptom orientated questionnaire (10) as well as the EORTC QLQ-OES18 questionnaire to assess the Gastrointestinal related Quality of life. In addition, we perform a radiological passage examination to assess the presence of late DGCE. These questionnaires, which are completed on days 5 and 10 as well as after 3 months, together with the radiographic examinations performed at the same time points, represent additional study-specific assessments. They would therefore not be performed in case of non-participation in the study.

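### Late DGCE is named an incidence after day 14 but is ascertained once, at 3 months: that is a point prevalence, and cases resolved before the visit are not counted

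*Protocol*

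**What the plan says.** The synopsis lists among the secondary endpoints the "Incidence of late DGCE (after more than 14 days postoperatively"). The synopsis objective asks whether dilatation "reduces the incidence of DGCE in the early postoperative course (until three months postoperatively").

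Section 3.2 turns the endpoint into a measurement: the "incidence of late DGCE measured using the symptom orientated DGCE questionnaire and a radiological passage examination after 3 months". Other places agree on that single time point:

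- Section 3.3: "After 3 months we assess the DGCE specific symptoms using the DGCE symptom orientated questionnaire".
- Synopsis, study procedures: "Additionally, a radiological passage will be performed after 3 months".
- Section 4.3: the purpose of the 3-month contrast examination is to assess whether late DGCE is present.
- Appendix 1: assessment columns at day 5, day 10 and 3 months, with none in between. The contrast passage is marked at 3 months only.

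Section 2 gives the consensus background: "Experts describe the following parameters for the presence of late DGCE (>14 days postoperatively"), namely at least two listed symptoms together with delayed contrast passage.

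On treatment, section 3.4 says that the balloon procedure "presents the current gold standard in the therapy of DGCE". Section 4.3 says that, when the course deviates from standard, "any necessary therapy is adapted according to" the patient's needs.

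**The concern.** An incidence counts everyone who develops the condition over a period. A single examination counts those who have it on that day. The two agree only if nobody who develops late DGCE after day 14 has recovered by 3 months.

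The protocol gives reason to expect that some will have recovered, because it describes an established therapy for the condition and allows therapy according to need. A patient who develops late DGCE in, say, week 4, is treated and is well at 3 months has no current symptoms and no delayed passage, and so is not a case.

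At stake is what the publication can say. A result headed incidence of late DGCE would understate how many patients had it. A difference between the arms in cases that arose and were treated would not appear in this endpoint.

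**Working it through.** **Step 1. Label against measurement.**

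| Element | What the protocol gives | Where |
|---|---|---|
| Name | incidence | synopsis; 3.2 |
| Period | beyond day 14; objective runs to 3 months | synopsis |
| Instruments | DGCE questionnaire and contrast passage | 3.2, 3.3, 4.3 |
| Time of reading | 3 months, once | synopsis, 3.2, 3.3, 4.3, Appendix 1 |
| Rule for cases arising and resolving earlier | none | – |

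The name and period describe cumulative occurrence. The instruments and timing give a point prevalence.

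**Step 2. Could recall on the questionnaire close the gap?** Its recall period is not given. Under the criteria in section 2, symptoms must be accompanied by delayed contrast passage. A patient who recalls earlier symptoms but whose conduit now empties normally would still not qualify.

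**Step 3. Do other records close it?** Section 4.3 takes interventions and complications from the charts, and Appendix 1 carries adverse events to 3 months. No sentence connects either to the late DGCE endpoint.

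**Step 4. The plan's own figure.** Section 5.1 uses 48% against 22%, α = 0.05 and 80% power. Taking α as two-sided, with mean proportion 0.35:

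n = [1.96·√(2 × 0.35 × 0.65) + 0.8416·√(0.48 × 0.52 + 0.22 × 0.78)]² / 0.26² = (1.322 + 0.546)² / 0.0676 ≈ 51.6, so 52 per arm. Then 52 / 0.9 = 57.8, so 58.

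Both stated numbers reproduce. They concern early DGCE and nothing here changes them.

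**Step 5. Illustration for late DGCE.** The protocol gives no late DGCE rate, no frequency or timing of treatment, and no resolution rate, so all inputs below are assumptions. Visit rate = true rate × (1 − share resolved). Power for n per arm, two-sided 0.05, with p̄ the mean of the two rates:

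Φ{ [ |p₁ − p₂|·√n − 1.96·√(2p̄(1 − p̄)) ] / √(p₁(1 − p₁) + p₂(1 − p₂)) }

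True rates 25% (control) and 10% (dilatation), same share resolved in both arms:

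| Resolved | Visit shows | Difference | Risk ratio | Power, 58 per arm | Power, 52 per arm |
|---|---|---|---|---|---|
| 0% | 25% v 10% | 15 points | 0.40 | 56.7% | 52.2% |
| 30% | 17.5% v 7% | 10.5 | 0.40 | 40.6% | 37.0% |
| 50% | 12.5% v 5% | 7.5 | 0.40 | 29.6% | 27.0% |
| 70% | 7.5% v 3% | 4.5 | 0.40 | 19.0% | 17.5% |

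The column for 52 per arm is the more relevant one, since section 5.1 allows for 10% attrition.

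Starting instead from 30% and 15% with 0%, 25%, 50% or 75% resolved, the difference is 15, 11.3, 7.5 or 3.8 points, and power at 52 per arm is 44.8%, 33.2%, 22.5% or 12.8%. The risk ratio stays at 0.50.

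**Step 6. Unequal resolved shares.** From 25% and 10%:

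- 50% of control and 25% of dilatation cases resolved: 25 × 0.50 = 12.5% and 10 × 0.75 = 7.5%; ratio 0.60.
- 75% and 25%: 6.25% and 7.5%; ratio 1.20, so the sign reverses.
- 25% and 50%: 18.75% and 5%; ratio 0.27, so the effect is exaggerated.

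The ratio can move either way, and nothing in the documents says which.

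**The case against.** The strongest reply is that the period in the synopsis is only a category label. Section 2 divides DGCE into early and late at day 14, and the parenthesis may repeat that division without promising continuous follow-up. All the procedural text agrees on one assessment at 3 months, and section 4.3 speaks of presence. On that reading the only fault is the word incidence. This reading is fair and it limits the point, but the endpoint then still needs its correct name, and the cases before 3 months remain uncounted.

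A reader might infer that the endpoint is biased toward no difference because controls, having more cases, would be treated more. The documents do not support that as stated. More cases in one arm is not a larger resolved share in that arm. With equal shares the risk ratio is unchanged, and only the absolute difference and the power fall. A distorted ratio needs unequal shares, for which there is no figure.

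Two other inferences go too far. The protocol ranks no secondary endpoint, so late DGCE is merely listed first. Nor does the protocol state that treated patients count as free of late DGCE. That follows from how it is measured.

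Finally, interim cases need not vanish altogether. Complication rates by Clavien-Dindo are a separate secondary endpoint, and charts and adverse event records may show them. This stands, and it is why the remedy is cheap. How endpoints are derived may also be set out in an analysis plan not shown here. The mismatch between name and measurement, however, is fixed in the protocol itself.

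**Conclusion.** The point holds as a mismatch of definition and needs no assumed number: as written, the protocol reports prevalence at 3 months under the name of incidence, and a case resolved before the visit is not counted. The consequence is an understated cumulative incidence, a smaller absolute difference and lower power for this endpoint.

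The size cannot be established from the documents. Under the assumed 25% and 10% with 30% to 70% resolved equally, the 15-point difference falls to between 10.5 and 4.5 points, and power at 52 per arm falls from 52.2% to between 37.0% and 17.5%. Even with complete capture, power under these assumptions would be only about one half. The trial was not sized for this endpoint, and that is not a fault.

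The primary endpoint, its analysis and the sample size are untouched. The change is worth making because it is small, and because interim events are easiest to record if the rule exists from the start.

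**What to change.** In section 3.2 and the synopsis:

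1. Name the questionnaire and contrast assessment prevalence of late DGCE at 3 months.
2. Also report by arm a cumulative incidence that counts any DGCE diagnosed, or any intervention for DGCE recorded, from day 15 to the 3-month visit. Take it from the chart and adverse event data already collected, extracted by staff blinded to arm.

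The cost is a sentence or two in each place and one REDCap field. No visit, examination or change to patient care is implied.

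The second measure has a real drawback. Charted diagnoses and treatment decisions may be influenced by staff who know the arm (section 3.3 notes that the operating surgeon is unblinded), and they may not meet the consensus criteria in section 2. Neither result should therefore replace the other. Report both side by side, each under its own name.
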